7.9.2 Efficacy Endpoints

7.9.2.1 Device success (VARC-2)

Device success is defined as meeting all of the following:

- Absence of procedural mortality, AND
- Correct positioning of a single prosthetic heart valve into the proper anatomical location, AND
- Absence of patient prosthesis-mismatch AND mean aortic valve gradient < 20 mmHg (or peak velocity < 3 m/sec), AND
- Absence of moderate or severe prosthetic valve regurgitation.

Components of device success will be reported on the procedure CRF, the echo core lab CRF at discharge, and CEC CRF:

- Procedural mortality will be defined as any death occurring within 30 days of implant or prior to hospital discharge.
- Correct positioning of the single prosthetic heart valve into the proper anatomical location will be reported by the investigator on the procedure CRF.
- Absence of patient-prosthesis mismatch will be derived from the echo core lab data at discharge. Patient prosthesis mismatch is defined in Section 7.9.2.4.
- Mean aortic valve gradient < 20 mmHg (or peak velocity < 3 m/sec) will be derived from the echo core lab CRF at discharge
- Absence of moderate or severe prosthetic valve regurgitation will be derived from the echo core lab CRF at discharge

The endpoint will be reported as the count and percentage of subjects achieving device success with two-sided 95% exact binomial confidence interval. Subjects will be defined as success if all components are met. Subjects will be defined as failure if any one component with available data is not met, regardless if data are available for all components. Subjects missing data for any components and not meeting criteria for failure will be considered to have a missing outcome. The numerator will include the number of subjects with device success and the denominator will include subjects evaluable for device success (known status of success or failure). The components of device success will also be summarized descriptively. The endpoint will be analyzed using the Implanted set.

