 - Peak aortic velocity ≤ 4 m/s and mean aortic gradient ≤ 40 mmHg, AND EOA < 0.8 cm², AND DVI < 0.25

Note: In the above, for subjects with BSA < 1.6 m², the EOA criteria for significant (moderate or severe) stenosis is < 0.6 cm². Additionally, for subjects with LVOT diameter > 2.5 cm, the DVI criteria for significant (moderate or severe) stenosis is < 0.2.

- Moderate or severe paravalvular regurgitation
- Moderate or severe transvalvular regurgitation
- Moderate or severe total regurgitation

Analysis of BVD will be based on data collected on the core lab CRF. The numerator for each time point will include the number of subjects meeting any of the components of BVD. The denominator will include any subject with BVD and subjects with no evidence of BVD having evaluable data for all 4 components. BVD will be summarized with frequency counts and percentages. The components of BVD will also be summarized. The analysis will be performed using the Implanted set.

Additional Outcome Measure 12 - Bioprosthetic valve failure (BVF)⁽²⁾ at 30 days, 6 months, 1 year

Bioprosthetic valve failure (BVF) is defined as meeting any of the following:

- Autopsy findings of bioprosthetic valve dysfunction, likely related to the cause of death, or valve-related death (i.e. any death caused by bioprosthetic valve dysfunction or sudden unexplained death following diagnosis of bioprosthetic valve dysfunction)
- Repeat intervention (i.e. valve-in-valve TAVI, paravalvular leak closure or SAVR following confirmed diagnosis of bioprosthetic valve dysfunction)
- Severe bioprosthetic valve dysfunction

A Kaplan-Meier analysis as described in Section 7.2 will be performed for BVF at 30 days, 6 months, and annually through 5 years. The analysis will use the Implanted set.

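### Device success and BVD accept a bad outcome on partial data but a good one only on complete data, so inclusion of partly observed subjects depends on the outcome; undetermined subjects should be counted and bounded

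*SAP*

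**What the plan says.** BVD (SAP 7.9.3, additional outcome measure 11) has four components: moderate or severe stenosis, and moderate or severe paravalvular, transvalvular and total regurgitation. The data source is single: "Analysis of BVD will be based on data collected on the core lab CRF". One positive component is enough for the numerator: "The numerator for each time point will include the number of subjects meeting any of the components of BVD". The denominator rule is not symmetric: "The denominator will include any subject with BVD and subjects with no evidence of BVD having evaluable data for all 4 components". BVD is reported as counts and percentages, with no confidence interval.

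Device success (SAP 7.9.2.1) draws on several forms: "Components of device success will be reported on the procedure CRF, the echo core lab CRF at discharge, and CEC CRF". To count as a success, a subject must pass every component. A failure needs less: "Subjects will be defined as failure if any one component with available data is not met, regardless if data are available for all components". Everyone else is set aside: "Subjects missing data for any components and not meeting criteria for failure will be considered to have a missing outcome". Subjects with a missing outcome leave the denominator. The percentage carries an exact binomial 95% interval.

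SAP 7.4 imputes no missing outcome data and promises the number analysed for each analysis. The components of both composites are also summarised. No bounds or other sensitivity analysis are planned for subjects whose composite is only partly observed.

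**The concern.** Take two subjects with the same component missing. The one with a bad finding elsewhere is counted; the one whose observed components are all good is dropped. The percentage then describes a group selected partly on the outcome.

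The second primary objective is to estimate event rates for endpoints of pivotal studies. Device success is the first-listed efficacy endpoint, and BVD is followed annually to 5 years. A rate shifted by the evaluability rule could be carried into pivotal planning, and the tables as planned would not show by how much.

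**Working it through.** The plan gives no expected BVD rate, device success rate or missing-data rate, and its sample size of 75 was not calculated. There is no figure to reproduce, so every rate below is an assumption.

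**Direction.** Every retained subject is classified correctly, so the reported rate R is the true rate among retained subjects. Let P be the full-data bad-outcome rate, d the fraction dropped and D the true bad-outcome rate among those dropped. Then P = (1−d)R + dD, which gives

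R − P = d(R − D).

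The bias is upward exactly when D < R.

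Suppose missingness is unrelated to outcome. For a given missing pattern, let q be the probability that an observed component is bad. Dropped subjects have all observed components good, so their bad-outcome rate is (P − q)/(1 − q), which is at most P. The bias is therefore zero or upward. It is zero when q = 0, which happens in two ways:
- every bad outcome arises through the missing component;
- for BVD, the whole echo is missing, because all four components then drop together.

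A missing discharge echo does not make q zero for device success, because death and positioning come from other forms.

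**Size.** Let block A be the part that can be missing, with bad rate a, and block B the part always observed, with bad rate b. The two are taken as independent. A is missing at rate mA when bad and m0 when good.

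R = [b + (1−b)a(1−mA)] / {[b + (1−b)a(1−mA)] + (1−a)(1−b)(1−m0)}, and P = 1 − (1−a)(1−b).

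BVD with 1% stenosis, 5% regurgitation and 10% missing stenosis data:
- P = 1 − 0.99×0.95 = 5.95%.
- R = 0.05855/(0.05855 + 0.84645) = 6.47%.
- Check: d = 0.095, D = 1.0%, and 0.095 × (6.47 − 1.0) = 0.52 points.

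With mA = m0:

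| Composite | a, b | P | R at 10% | R at 30% |
|---|---|---|---|---|
| BVD | 1%, 3% | 3.97% | 4.29% | 5.19% |
| BVD | 1%, 5% | 5.95% | 6.47% | 7.92% |
| BVD | 3%, 0% | 3.00% | 3.00% | 3.00% |
| Device failure | 5%, 5% | 9.75% | 10.25% | 11.64% |
| Device failure | 15%, 5% | 19.25% | 19.70% | 20.94% |
| Device failure | 15%, 10% | 23.50% | 24.34% | 26.64% |

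The excess runs from 0 to 0.8 points at 10% missing and from 0 to 3.1 points at 30%. With the whole discharge echo missing in 10% (20% echo failure, 5% death or malposition), device failure moves from 24.0% to 24.4%.

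**Reversal.** Take device failure with a = 15% (patient-prosthesis mismatch), b = 5% and m0 = 10%. The bias changes sign once mA exceeds 13.5%. At mA = 20%, R = 0.164/(0.164 + 0.72675) = 18.4% against P = 19.25%. BVD with a = 2%, b = 5% and m0 = 10% needs mA above 36%.

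**Bounds at 10% missing.** For BVD (1%, 5%) they are 5.86% with missing as good and 5.86 + 9.5 = 15.4% with missing as bad. For device failure (15%, 5%) they are 17.8% and 27.3%.

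**When stenosis is already settled.** Two of the three stenosis criteria need peak velocity above 4 m/s or mean gradient above 40 mmHg; the third needs DVI below 0.25. If velocity is at most 4, gradient at most 40 and DVI at least 0.25, all three fail whatever EOA is. Protocol 13.3.5 derives DVI from the two VTIs alone, so it survives a missing LVOT diameter. The note for LVOT diameter above 2.5 cm lowers the DVI limit to 0.2 and does not alter this conclusion. Mismatch is different: it needs EOA, so a missing LVOT diameter does leave it open.

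**Scale.** With 75 subjects, 4 BVD cases and 8 others undetermined, 4/75 = 5.3% becomes 4/67 = 6.0%. The exact 95% interval for 4/75 is 1.5% to 13.1%.

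**The case against.** The best defence is that the rule is logically sound for failures. One failed component settles an all-of-the-following endpoint, so discarding that subject would throw away a known result. A subject who dies before a discharge echo (due no earlier than 12 hours after the procedure) is a certain failure. Suppose 75 are implanted, with 5 echo failures and 2 such deaths: the SAP gives the correct 7/75 = 9.3%, while complete cases give 5/73 = 6.8%. This stands, and it rules out complete cases as the main analysis.

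It is also fair that analysed numbers and components will be reported, that neither composite is a key study endpoint, and that the study is descriptive. These points limit the importance. They do not recover the composite for dropped subjects.

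A reader might infer more than the documents support:
- **That only good outcomes are removed, so the rates are always too high.** True failures hidden in the missing component are removed too, and the bias can be zero or negative.
- **That a 5% BVD rate would read 5.5%, 6.2% or 7.0% with EOA missing in 10%, 20% or 30%.** The arithmetic, 0.05/(0.05 + 0.95(1−m)), is right. But it assumes a missing EOA always makes stenosis unevaluable. EOA is an input to stenosis, not one of the four components, and the SAP does not say this.
- **That an exact interval for BVD is miscentred.** Only device success has one.
- **That the 5-year BVD trend will be distorted.** Nothing in the documents shows that missingness will vary by visit.

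**Conclusion.** The asymmetry is real in both composites. If missingness is unrelated to outcome, the reported BVD and device-failure rates are unbiased or too high. Under the assumed rates, the excess is about 0 to 1 point at 10% missing and up to about 3 points at 30%. That is small beside the sampling uncertainty at 75 subjects. Both direction and size depend on missingness that the documents do not describe. This is a cheap improvement to rates meant for pivotal planning, not an error that undermines the study.

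**What to change.** Amend SAP 7.9.2.1 and 7.9.3 (measure 11) as follows:
1. Keep known device failures and known BVD in the main rate, as now.
2. Define a component as evaluable when the available data logically determine it. Subjects with peak velocity ≤ 4 m/s, mean gradient ≤ 40 mmHg and DVI ≥ 0.25 then count as free of stenosis even if EOA is missing, and stay in the BVD denominator if the regurgitation grades are available.
3. Report the number left undetermined because of partial data, by visit. For both composites, give the rate with these subjects counted all as good and all as bad. Show complete cases only as a sensitivity analysis.

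The cost is SAP wording, a little programming, a few more table rows, and a range beside what would otherwise be a single rate. No new data are needed.

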7.9.4 Subgroup Analysis

Subgroup analysis will be performed for the key study endpoints for exploratory purposes in the following subgroups:

1. Baseline Peak GLS \geq median value and $<$ median value
2. Baseline NT-proBNP \geq median value and $<$ median value

As the study is intended to inform the design for a future pre-market study, subgroup analyses need not be limited to those defined above and additional subgroup analyses may be performed to better understand the safety and efficacy results in these two groups of AS patients.

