Medtronic is sponsoring this feasibility study to evaluate the safety and efficacy of the Medtronic Evolut PRO+ TAVR system in patients with severe asymptomatic aortic AS. There are important differences in the inclusion/exclusion criteria for this study compared to the EARLY TAVR study. The EARLY TAVR study requires ETT to establish the absence of symptoms. While this is consistent with current guidelines, it is important to note that ETT is not feasible in a considerable number of elderly patients. Therefore, this study will allow patients irrespective of the ability to perform ETT, provided they have additional markers of LV dysfunction that may prove to be more sensitive than LVEF for identification of LV dysfunction attributable to AS.

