5.2 Rationale

The safety and effectiveness of the Medtronic self-expanding Evolut R and PRO TAVR systems have been established through rigorous clinical evaluation in patients with severe symptomatic AS. However, contemporary evidence from scientific literature indicates patients with a degree of AS outside of the current TAVR indications are also at risk for serious adverse effects of AS. The risk and benefits of TAVR in patients with severe asymptomatic AS has not been well studied in prospective clinical studies, although clinical trials have recently been initiated in AS patients using the balloon expandable TAVR system.

This feasibility study is intended to obtain initial procedural safety and efficacy data on the use of the Medtronic self-expanding Evolut PRO+ TAVR system in this group of AS patients. Data from this study will be used to inform the design of future pivotal studies to expand the current indications to include this population. Specifically, the study objectives and associated endpoints are intended to fully characterize the spectrum of AS severity, LV function, and symptomology, provide information on event rates for pivotal sample size estimations, and refine the entrance criteria for future pivotal studies. The single arm design and sample size of 75 subjects is consistent with the views and opinions of US FDA physicians regarding feasibility studies in the development of percutaneous heart valves⁵⁵ and will provide adequate information to inform a pivotal study. A comprehensive bench testing protocol has been completed on the Evolut PRO+ system and is generalizable to the study population. The clinical study endpoints are relevant and consistent with the study objectives. The design of this study is based on clinical evaluation and aligned with risk assessment results.

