10.1 General Aspects of Analysis

Data analysis will be performed by Medtronic clinical personnel per departmental SOP and according to the Statistical Analysis Plan developed for this study. As this is a descriptive study, there are no prospectively developed study hypotheses or powered clinical endpoints. There will be two analysis sets: 1) the Attempted Implant set, and 2) the Implanted set:

Attempted Implant. The attempted implant data set will include all subjects with an attempted implant, where an attempted implant is defined as when the subject is brought into the procedure room and any of the following have occurred: anesthesia administered, vascular line placed, TEE placed or any monitoring line placed. Day 0 is the date of first attempted procedure.

Implanted. The implanted data set includes of all subjects with an attempted implant where the study device is implanted, defined as when the TAV is fully released from the DCS. Day 0 is the date of first attempted procedure.

Information on the analysis data sets specific to the study endpoints and outcome measures are provided in Section 10.4. Data from all geographies and active centers will be included in the analyses; there are no planned poolability analyses (e.g. by gender, race, geography).

Baseline demographic and clinical variables will be summarized for attempted implant analysis set. The subjects' baseline characteristics will be summarized with standard descriptive summary statistics, including counts and percentages for categorical variables, and mean, standard deviation, median, first and third quartiles, minimums and maximums for continuous variables.

Subject disposition will be illustrated in a flow diagram. Subject visits will be tabulated and compliance to visit schedule and visit windows will be summarized, and attrition will be identified and summarized. Every effort will be undertaken to minimize missing data. Missing (accidentally, due to withdrawal, missing follow-up or loss to follow-up, etc.), unused and spurious data will remain identifiable in the database. Data from subjects that cannot be analyzed for a specific variable will be displayed as missing. All analyses will be based on available data and missing data will not be imputed. Subgroup analyses may be performed (but are not limited to) include the following subject groups:

1. Baseline Peak GLS \geq median value and $<$ median value
2. Baseline NO-proBNP \geq median value and $<$ median value

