Subgroup analyses will be performed at minimum for the following key study endpoints at 30 days and 6 months, where applicable: all-cause mortality, stroke, valve-related dysfunction requiring repeat procedure, new PPI, cardiovascular and heart failure hospitalizations, heart failure events, change in KCCQ, change in 6MWT, and change in cardiac function by echo.

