7.8 Interim Analyses

An initial analysis is planned when the first 50 to 75 implanted subjects have completed his/her 6 month follow-up; however initial analyses may be performed earlier if enrollment is slower than expected. Initial analyses will assess all safety and efficacy endpoints based on available data. The analysis will be descriptive and no formal interim analyses are planned for the purpose of early stopping or sample size re-estimation.

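### Cheap improvement: baseline GLS and NT-proBNP are analysed only by an exploratory median split, which gives up information and cannot show how outcome varies across the marker range

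*SAP*

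**What the plan says.** SAP 7.9.4 introduces the marker analysis with "Subgroup analysis will be performed for the key study endpoints for exploratory purposes in the following subgroups". The two subgroups are baseline peak GLS and baseline NT-proBNP, each at or above versus below the median. The section adds that "subgroup analyses need not be limited to those defined above and additional subgroup analyses may be performed", but specifies no others.

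Protocol 10.1 lists the same two splits under permissive wording, "Subgroup analyses may be performed (but are not limited to) include the following subject groups". It then becomes firmer: "Subgroup analyses will be performed at minimum for the following key study endpoints at 30 days and 6 months".

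Neither document gives a numeric cut, says which analysis set supplies the median, or pre-specifies a model or plot with the marker as a continuous variable.

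On purpose, Protocol 5.2 says the objectives and endpoints are intended, among other things, to "refine the entrance criteria for future pivotal studies"; SAP section 4 says the same. Protocol 3.1 explains that subjects unable to exercise may enter if they have "additional markers of LV dysfunction that may prove to be more sensitive than LVEF"; that paragraph does not name GLS or NT-proBNP.

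**The concern.** Judging whether a marker could serve in an entry criterion requires seeing how outcome changes over the marker's range: whether the relation is gradual, flat or abrupt, and roughly where it changes. A single split at the median compares two averages. It treats subjects just either side of the cut as different and everyone within a half as alike. It therefore cannot show the shape of the relation or compare one possible cut-point with another.

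It also uses the data inefficiently when the relation is gradual, which matters with at most 75 implanted subjects and halves of about 37. At stake is a weaker basis for pivotal design than the same data could give. The validity of any reported result is not in question.

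**Working it through.** The documents state no power, precision or information figure for the subgroups, and the sample size of 75 was not derived statistically (Protocol 10.7, SAP section 6). There is no figure to reproduce, so the check asks how much a median split gives up.

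**Inputs.** From the documents: 75 implanted subjects, and an initial analysis at 50 to 75 (SAP 7.8; Protocol 10.3 says the first 50). Assumed, because the documents do not give them: the marker's distribution and the form of its relation to outcome.

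**Information kept.** For an outcome linear in marker X, the efficiency of a median split relative to the continuous marker is the squared correlation of X with the indicator D that X is at or above its median.

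- Normal X (SD 1): cov(X, D) = 1/√(2π) and var(D) = 1/4, so the squared correlation is [1/(2π)]/(1/4) = 2/π = 0.637.
- Loss = 1 − 0.637 = 36.3%.
- Effective size: 0.637 × 75 = 47.7, about 48; 0.637 × 50 = 31.8, about 32.
- Uniform X on 0 to 1: cov = 3/8 − 1/4 = 1/8, var(X) = 1/12, so the squared correlation is (1/64)/(1/48) = 0.75.

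**Sensitivity to the assumptions** (non-normal rows agree with 1,000,000 simulated draws, except the log-linear and step rows, which follow directly):

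| Marker and relation | Loss |
|---|---|
| Uniform, linear | 25% |
| Normal, linear | 36% |
| Lognormal, linear in the log of the marker | 36% |
| t with 5 df, linear | 46% |
| Lognormal, log-SD 0.5, linear on raw scale | 48% |
| Lognormal, log-SD 1, linear on raw scale | 73% |
| Step exactly at the median | 0% |

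**Power as a yardstick** (20,000 simulated trials, normal marker, linear relation, two-sided 5%; the study itself plans no hypothesis tests):

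| n | True correlation | Continuous | Median split |
|---|---|---|---|
| 75 | 0.2 | 40% | 27% |
| 75 | 0.3 | 75% | 55% |
| 75 | 0.4 | 95% | 81% |
| 50 | 0.3 | 57% | 39% |

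If instead the truth is a step of 0.65 SD near the median, the order reverses at n = 75: 71% for the split, 58% for the linear term.

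**Precision of the halves.** The difference detectable with 80% power in a 37 versus 38 split is (1.96 + 0.84) × √(1/37 + 1/38) = 0.65 SD. For events, zero in 37 subjects leaves an exact two-sided 95% upper limit of 1 − 0.025^(1/37) = 9.5%.

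These efficiencies treat the marker alone. With the endpoint's own baseline value also in the model, they are approximate.

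**The case against.** The strongest reply is that the study is descriptive, the subgroups are labelled exploratory, and SAP 7.9.4 leaves further subgroup analyses open. That stands, and it is why this is an improvement and not an error. It does not remove the point. A slope with a confidence interval is equally descriptive, the SAP already reports intervals for changes from baseline, and the open clause specifies nothing. An analysis named before the data are seen carries more weight than one chosen afterwards.

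A second reply is that limited precision comes mainly from n = 75. This is partly right: at a correlation of 0.2 even the continuous analysis has only 40% power. A third is that six of the nine key endpoints listed in SAP section 4 are events, where a model may add little. That stands and limits the fix.

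Stronger readings are tempting but not supported:

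- A reader might infer that the median is recomputed at each analysis. Both documents are silent on this; they describe when analyses occur, such as "An initial analysis is planned when the first 50 to 75 implanted subjects have completed his/her 6 month follow-up", and do not say how the cut is carried forward. Once enrollment is complete, further follow-up does not by itself move a baseline median.
- A reader might infer that the subgroups exist to set entry criteria. The documents give that aim to the objectives and endpoints as a whole.
- A reader might infer that the plan yields no usable threshold. The observed median would be one candidate value, and other cuts are permitted. What the split cannot do is compare candidates.

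**Conclusion.** The point holds as a cheap improvement. The only pre-specified analysis of baseline peak GLS and NT-proBNP is a median split, which cannot describe how outcome varies across the marker range or compare cut-points. For a roughly normal marker with a linear effect, the loss is about 36% of the information, 75 subjects acting like about 48. Neither condition comes from the documents. Over the alternatives examined, the loss runs from 25% to about 73%, and it is zero if the true effect is a step at the median, where the split outperforms a straight line.

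The benefit falls mainly on KCCQ, 6MWT, LVEF, GLS and E:e'. Because the study has one arm, either analysis describes how the marker relates to outcome after TAVR and not how it modifies benefit over no TAVR.

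**What to change.** In SAP 7.9.4:

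- For the continuous key endpoints (KCCQ, 6MWT, LVEF, peak GLS, E:e'), make the main exploratory analysis a regression of the 6-month value on its own baseline value plus baseline GLS or log NT-proBNP. Report the marker slope with 95% confidence interval and a scatter plot.
- For 6-month GLS with GLS as the marker, the own-baseline value and the marker are the same variable, so baseline GLS is the single covariate.
- Keep the median-split tables as a display and state the numeric median used in each report.
- Leave event endpoints as median-split displays unless there are enough events for a one-covariate model.

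The cost is a few sentences in the SAP and a few extra models on data already collected. The downsides are a linearity assumption, to be checked on the scatter plot, and little gain for sparse event endpoints.

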The primary objectives of this feasibility study are as follows:

1. Characterize the spectrum of cardiac function, symptomology, and severity of aortic stenosis in the study populations,
2. Estimate event rates for potential safety and effectiveness endpoints to be evaluated in pivotal studies for the proposed patient populations, and
3. Evaluate the effect of TAVR on cardiac function, functional capacity, effort tolerance, and patient-reported quality of life in the study populations.

The study objectives and associated endpoints are intended to fully characterize the spectrum of aortic stenosis (AS) severity, left ventricular (LV) function, and symptomology of patients with moderate

symptomatic and severe asymptomatic AS, provide information on event rates for pivotal sample size estimations, and refine the entrance criteria for future pivotal studies. The full list of protocol defined endpoints are detailed in Section 7.9. Of the protocol defined endpoints, the following key study endpoints have been identified:

Key Safety Endpoints:

- All-cause mortality at 30 days and 6 months
- All stroke (disabling and non-disabling) at 30 days and 6 months
- Valve-related dysfunction requiring repeat procedure at 30 days and 6 months
- New permanent pacemaker implant (PPI) at 30 days and 6 months

Key Efficacy Endpoints:

- Cardiovascular and heart failure hospitalizations at 30 days and 6 months
- Heart failure events at 30 days and 6 months
- Change in Kansas City Cardiomyopathy Questionnaire (KCCQ) at 6 months
- Change in Six-Minute Walk Test (6MWT) at 6 months
- Change in cardiac function by echo (LVEF, Peak GLS, E:e') at 6 months

5. Investigation Plan

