5.1 Study Design

This is a prospective, descriptive, interventional, multi-center, single-arm, pre-market, feasibility study. The study will involve up to 75 subjects with severe, asymptomatic AS implanted using the Medtronic Evolut PRO+ TAVR system among up to 25 centers in the United States, Canada, Europe, Israel, Australia, and New Zealand. As not all patients consented for evaluation will go forward to implantation, the number of subjects consented for the study is expected to be higher than 75 (up to 150). No site will implant more than 15 total subjects without prior authorization from Medtronic in order to minimize bias.

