7.9.2.9 Change in peak global longitudinal strain (GLS) from baseline at 6 months

Peak global longitudinal strain (GLS) will be analyzed according to the data collected on the core lab echo CRF. At each time point, peak GLS will be summarized descriptively as continuous data. Change from baseline will be summarized descriptively along with two-sided 95% confidence interval and p-value from a paired t-test. The endpoint will be analyzed using the Implanted set.

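### Summarising change in GLS by halves of the same baseline GLS builds in regression to the mean, which a single-arm table cannot separate from a real difference in response

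*SAP*

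**What the plan says.** SAP 7.9.4: "Subgroup analysis will be performed for the key study endpoints for exploratory purposes in the following subgroups". The first listed subgroup is "Baseline Peak GLS" at or above versus below its median; the second is NT-proBNP, split the same way.

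SAP section 4 names among the key efficacy endpoints at 6 months "Change in cardiac function by echo (LVEF, Peak GLS", with E:e' as the third echo measure. Protocol 10.1 sets a minimum list of endpoints for subgroup analysis that ends with "change in KCCQ, change in 6MWT, and change in cardiac function by echo".

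For change in peak GLS, SAP 7.9.2.9 says: "Change from baseline will be summarized descriptively along with two-sided 95% confidence interval and p-value from a paired t-test". It adds: "The endpoint will be analyzed using the Implanted set". SAP 7.9.4 gives no separate method for subgroups.

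On design, SAP 5.1 says: "This is a prospective, descriptive, interventional, multi-center, single-arm, pre-market, feasibility study".

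Neither document mentions regression to the mean, a replicate baseline GLS or a correction for measurement reliability.

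**The concern.** A subject falls in the worse half partly because true strain is poor and partly because that day's reading was unfavourable. The unfavourable part does not persist, so on average these subjects move back towards the centre at 6 months whatever TAVR does. The better half moves the other way. Because change is computed from the reading that defined the halves, this drift is counted as response. A single-arm study has no untreated group in which to observe it.

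The direction is fixed: impaired strain appears to gain more. SAP 7.9.4 ties its subgroup analyses to the design of a later study, and the stated aims of this study include sharpening the entry criteria of the pivotal trials. A table that leans towards one answer by construction is a poor basis for that discussion.

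**Working it through.** The plan has no figure to reproduce. It gives no SD for GLS, no baseline-to-6-month correlation and no effect size, and the 75 subjects were not derived by a sample-size formula (SAP section 6).

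**Inputs from the documents**
- Split: observed median of baseline peak GLS (SAP 7.9.4).
- Outcome: 6-month GLS minus that same baseline, with paired t-test (SAP 7.9.2.9).
- Number: up to 75 implanted, about 37 or 38 per half. The initial analysis may come at 50, giving 25 per half (SAP 5.4). Available data only (SAP 7.4).

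**Assumptions, not in the documents**
- SD of GLS 2 to 4 strain points, equal at both visits; bivariate normal values.
- rho, the correlation between baseline and 6-month GLS when response does not vary between subjects, 0.6 to 0.9.

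**Formula**
1. With a median split, mean baseline in each half lies sqrt(2/π) × SD = 0.798 × SD from the overall mean.
2. Expected 6-month distance from the overall mean is rho times that.
3. Spurious change per half is 0.798 × (1 − rho) × SD, with opposite signs in the two halves.
4. The gap between halves is 2 × 0.798 × (1 − rho) × SD = 1.596 × (1 − rho) × SD. It is zero only if rho = 1.

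**Expected false gap, in strain points**

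| rho | SD 2 | SD 3 | SD 4 |
|---|---|---|---|
| 0.9 | 0.32 | 0.48 | 0.64 |
| 0.8 | 0.64 | 0.96 | 1.28 |
| 0.7 | 0.96 | 1.44 | 1.91 |
| 0.6 | 1.28 | 1.91 | 2.55 |

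**Check by simulation** (6,000 trials per setting, SD 3, no true change in anyone). At N = 75 the mean gap was 0.47, 0.94, 1.42 and 1.89 points for rho 0.9, 0.8, 0.7 and 0.6, close to the formula. If the paired t-test of SAP 7.9.2.9 is repeated within each half, the worse half gives p < 0.05 in about 19%, 33%, 47% and 60% of trials, against a nominal 5%. At N = 50 the rates are about 14%, 23%, 34% and 44%.

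**With a true uniform benefit.** If every subject improves by 1.0 point (SD 3, rho 0.8), the halves should show 1.0 ± 0.798 × 0.2 × 3 = 1.0 ± 0.48. The simulation gave 1.47 in the worse half and 0.52 in the better half: an apparent near-threefold difference where none exists.

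**Alternatives under the same null settings.** Splitting on an independent baseline measurement, or on the mean of baseline and 6-month GLS (Oldham), brought the gap to within 0.02 points of zero and the worse-half rejection rate to about 4% to 6%.

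**The case against.** The strongest reply is that little rides on this one cell. The subgroup analysis is labelled exploratory, SAP 7.5 disclaims formal testing, and no contrast between halves, interaction test or decision rule is specified. A reader might infer that the halves will be formally compared, or that a GLS entry threshold will be set from the result. The documents support neither. They plan side-by-side summaries, and the aim of refining entry criteria is attached to the study's objectives and endpoints, not to this table. Even the within-half p-values assume that the output of SAP 7.9.2.9 is repeated by subgroup, which SAP 7.9.4 does not say. All of this stands and limits the severity. It does not remove the bias from the two half-specific changes.

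A reader might also call the analysis mandatory. The wording is mixed: Protocol 10.1 introduces the subgroups as optional, then requires the listed endpoints as a minimum, and SAP 7.9.4 says the analysis will be done. It is planned, but the wording is not uniform.

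Another tempting inference is that the better half will appear to deteriorate. That follows only if the average effect is nil; otherwise it merely improves less.

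The protocol does work to limit GLS error: same vendor and software for serial exams where feasible (13.3.2), acquisition and tracking standards (13.3.4.5) and core-lab values as primary data (13.3.5). These raise rho and shrink the gap but cannot eliminate it. An observed correlation would also reflect genuine variation in response, so not all of 1 − rho from real data would be error.

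Finally, Oldham's method is not neutral if responses vary. With SD 3, rho 0.8 and an assumed response SD of 1.5 independent of baseline, the 6-month variance is 9 + 2.25 = 11.25. The covariance of change with the mean is then (11.25 − 9)/2 = 1.125, a correlation of about +0.16 where there is no dependence. Nor can a mean that includes the 6-month value serve as an entry criterion. Both points stand, so Oldham belongs only in a sensitivity analysis.

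**Conclusion.** The point holds, within limits. The planned summary of change in peak GLS by baseline-GLS half is biased in a known direction. The existence and direction of the bias follow from the design unless baseline and 6-month GLS correlate perfectly. Its size is not known from the documents: about 0.3 to 2.6 points over the assumed ranges, and 0.48 to 1.44 at SD 3 with rho from 0.9 to 0.7.

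The plan's table could not distinguish this artefact from a real difference in response by baseline strain, which may also exist.

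It would be wrong to infer that the overall GLS result or the subgroup plan as a whole is unsound. The overall change in GLS involves no split and is untouched. Change in NT-proBNP is not a key endpoint, so the second split has no matching overlap. The direct problem is confined to one endpoint within one split.

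**What to change.** In SAP 7.9.4 and Protocol 10.1:
- Exclude change in peak GLS, with its paired-t p-value, from the baseline-GLS split. Report the 6-month GLS level by baseline-GLS half instead, with a sentence saying that subtracting baseline from these levels reintroduces regression to the mean.
- Report change in GLS by the NT-proBNP split.
- If dependence of GLS change on baseline function is wanted, split on a separately measured baseline already collected: longitudinal systolic function by CMR (Protocol 13.5), accepting the loss of subjects in whom CMR is contraindicated. Alternatively, use Oldham's method as a sensitivity analysis and state its equal-variance assumption.
- Keep the GLS split for the other key endpoints, noting that LVEF and E:e' come from the same echo and may share some error with baseline GLS.

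The cost is wording and one table row, with no new data, visits or subjects. What is lost is the simple row of GLS change by baseline-GLS half.
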